##### Target Lesions

When more than one measurable tumor lesion is present at baseline all lesions up to a maximum of 5 lesions total (and a maximum of 2 lesions per organ) representative of all involved organs should be identified as target lesions and will be recorded and measured at baseline. Target lesions should be selected on the basis of their size (lesions with the longest diameter), be representative of all involved organs, but in addition should be those that lend themselves to reproducible repeated measurements. Note that pathological nodes must meet the criterion of a short axis of  $\geq 15$  mm by CT scan and only the short axis of these nodes will contribute to the baseline sum. All other pathological nodes (those with short axis  $\geq 10$  mm but  $< 15$  mm) should be considered non-target lesions. Nodes that have a short axis  $< 10$  mm are considered non-pathological and should not be recorded or followed. At baseline, the sum of the target lesions (longest diameter of tumor lesions plus short axis of lymph nodes: overall maximum of 5) is to be recorded.

After baseline, a value should be provided on the CRF for all identified target lesions for each assessment, even if very small. If extremely small and faint lesions cannot be accurately measured but are deemed to be present, a default value of 5 mm may be used. If lesions are too small to measure and indeed are believed to be absent, a default value of 0 mm may be used.

*Non-target Lesions*

All non-measurable lesions (or sites of disease) plus any measurable lesions over and above those listed as target lesions are considered non-target lesions. Measurements are not required but these lesions should be noted at baseline and should be followed as “present” or “absent”.

*Response*

All patients will have their BEST RESPONSE from the start of study treatment until the end of treatment classified as outlined below:

*Complete Response (CR)*: disappearance of target and non-target lesions and normalization of tumor markers. Pathological lymph nodes must have short axis measures <10 mm (Note: continue to record the measurement even if <10 mm and considered CR). Residual lesions (other than nodes <10 mm) thought to be non-malignant should be further investigated (by cytology, specialized imaging, or other techniques as appropriate for individual cases) before CR can be accepted. Confirmation of response is only required in non-randomized studies.

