*Partial Response (PR)*: at least a 30% decrease in the sum of measures (longest diameter for tumor lesions and short axis measure for nodes) of target lesions, taking as reference the baseline sum of diameters. Non target lesions must be non-PD. Confirmation of response is only required in non-randomized studies.

*Stable Disease (SD)*: Neither sufficient shrinkage to qualify for PR, nor sufficient increase to qualify for PD taking as reference the smallest sum of diameters on study.

*Progressive Disease (PD)*: at least a 20% increase in the sum of diameters of measured lesions taking as references the smallest sum of diameters recorded on study (including baseline) AND an absolute increase of  $\geq 5$  mm. Appearance of new lesions will also constitute progressive disease (including lesions in previously unassessed areas). In exceptional circumstances, unequivocal progression of non-target disease may be accepted as evidence of disease progression, where the overall tumor burden has increased sufficiently to merit discontinuation of treatment or where the tumor burden appears to have increased by at least 73% in volume. Modest increases in the size of one or more non-target lesions are NOT considered unequivocal progression. If the evidence of PD is equivocal (target or non-target), treatment may continue until the next assessment, but if confirmed, the earlier date must be used.

*Confirmatory measurement/duration of response*

*Confirmation*: In non-randomized trials where response is the primary endpoint, confirmation of PR and CR is required to ensure responses identified are not the result of measurement error. This will also permit appropriate interpretation of results in the context of historical data where response has traditionally required confirmation in such trials. However, in all other circumstances, i.e. in randomized trials (phase II or III) or studies where stable disease or progression are the primary endpoints, confirmation of response is not required since it will not add value to the interpretation of trial results. However, elimination of the requirement for response confirmation may increase the importance of central review to protect against bias, in particular in studies which are not blinded.

In the case of SD, measurements must have met the SD criteria at least once after study entry at a minimum interval (in general not less than 6–8 weeks) that is defined in the study protocol.

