**Table 9 : iRECIST best overall response**

TPR1	TPR2	TPR3	TPR4	TPR5	iBOR
iCR	iCR, iPR, iUPD, NE	iCR, iPR, iUPD, NE	iUPD	iCPD	iCR
iUPD	iPR, iSD, NE	iCR	iCR, iPR, iSD, iUPD, NE	iCR, iPR, iSD, iUPD, iCPD, NE	iCR
iUPD	iPR	iPR, iSD, iUPD, NE	iPR, iSD, iUPD, NE, iCPD	iPR, iSD, iUPD, NE, iCPD	iPR
iUPD	iSD, NE	PR	iPR, iSD, iUPD, NE	iPR, iSD, iUPD, iCPD, NE	iPR
iUPD	iSD	iSD, iUPD, NE	iSD, iUPD, iCPD, NE	iSD, iUPD, ICPD, NE	iSD
iUPD	iCPD	Anything	Anything	Anything	iCPD
iUPD	iUPD	iCPD	Anything	Anything	iCPD
iUPD	NE	NE	NE	NE	iUPD

- Table assumes a randomised study where confirmation of CR or PR is not required.
- NE = not evaluable that cycle.
- Designation "I" for BOR can be used to indicate prior iUPD to aid in data interpretation.
- For patients with non-target disease only at baseline, only CR or non-CR/non-PD can be assigned at each TPR but is not shown in the table for ease of presentation.

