### **7.8.3 Best overall response, objective response, and disease control rate (DCR)**

OR is defined as the best overall response during the whole study period equal to PR or complete response (CR) according to RECIST [Eisenhauer et al] or as best overall response during the whole study period equal to immune partial response (iPR) or immune complete response (iCR) according to iRECIST. No confirmation of PR/CR and iPR/ iCR is required.

The ORR [%] is defined as the relative number of patients achieving OR according to iRECIST/RECIST in the respective cohort. The DCR [%] is defined as the relative number of patients achieving at least one assessment of iCR, iPR, or iSD according to iRECIST in the respective cohort or as the relative number of patients achieving at least one assessment of CR, PR, or SD according to RECIST.

The ORR/DCR according to iRECIST/RECIST will be summarized with two-sided 95% exact Clopper-Pearson CIs for binomial proportions by cohort.

The best overall response according to RECIST will be summarized by cohort, using the following categories and hierarchy: OR (RECIST) with subcategories CR and PR, SD, PD, not evaluable.

The best overall response according to iRECIST will be summarized by cohort using the following categories and hierarchy: OR (iRECIST) with subcategories iCR, iPR, iSD, iUPD, iCPD, not evaluable.

The disease control according to RECIST will be summarized by cohort, using the following categories and hierarchy: disease control (RECIST) with subcategories CR, PR, and SD, and PD, not evaluable.

The disease control according to iRECIST will be summarized by cohort using the following categories and hierarchy: disease control (iRECIST) with subcategories iCR, iPR, and iSD, and iUPD, iCPD, not evaluable.

The maximal shrinkage in tumor burden (i.e. maximal percentage decrease in sum of longest diameter compared to baseline = relative change from baseline) will be displayed

in a waterfall plot. The bars will be colored according to best overall response according to RECIST/iRECIST. Two different colors will be used for PD with new lesion and PD without new lesion. iUPD and iCPD will have the same color. Waterfall plots will be provided for Cohort 2A, Cohort 2B, Cohort 2, non-randomized, for Cohort 3A, Cohort 3B, Cohort 3, and Cohort 2A-I, Cohort 2A-II, and Cohort 2A-III, randomized, and for patients fulfilling and not fulfilling extended in/exclusion criteria (see Section 6.6) of Cohorts 2A, non-randomized.

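### SAP 7.8.3 counts unconfirmed responses in every cohort while Protocol 12.1 gives two different confirmation rules; a confirmed ORR should stand beside the planned one in the non-randomized cohorts

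*SAP*

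**What the plan says.** SAP 7.8.3 defines objective response as a best overall response of PR or CR (RECIST 1.1), or iPR or iCR (iRECIST), over the whole study period. It adds "No confirmation of PR/CR and iPR/ iCR is required". The rate is then formed cohort by cohort: "The ORR [%] is defined as the relative number of patients achieving OR according to iRECIST/RECIST in the respective cohort". The rule is the same for randomized and non-randomized cohorts.

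Protocol 3.2.2 lists ORR among the other secondary endpoints and refers to Section 12.1 for the criteria. Section 12.1 speaks to confirmation in three places:

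- The CR and PR definitions in the RECIST 1.1 part each end with the sentence "Confirmation of response is only required in non-randomized studies".
- The later paragraph on confirmation is narrower: "In non-randomized trials where response is the primary endpoint, confirmation of PR and CR is required". Elsewhere, it says, "confirmation of response is not required since it will not add value to the interpretation of trial results".
- The iRECIST best-overall-response table (Table 9) carries the note "Table assumes a randomised study where confirmation of CR or PR is not required".

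The confirmation paragraph also cautions that "elimination of the requirement for response confirmation may increase the importance of central review to protect against bias", with unblinded studies singled out.

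**The concern.** The cohorts in question have no randomized comparator, so their ORR can only be judged against outside experience. The protocol gives this as one purpose of confirmation: "This will also permit appropriate interpretation of results in the context of historical data where response has traditionally required confirmation in such trials". Section 1.2 itself cites two checkpoint-inhibitor ORRs in adrenocortical carcinoma, 23.1% and 6.0%, which a reader will naturally set beside the result for Cohort 2A.

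Without confirmation, a single scan that crosses the PR threshold through measurement error or a favourable local reading counts in full. Unscheduled and post-treatment scans also count (SAP 7.8.1), so there are more occasions for this to happen. Time-to-OR and duration of response start from the same unconfirmed event (SAP 7.8.4 and 7.8.5).

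At stake is how a secondary endpoint in small single-arm cohorts is interpreted. No primary endpoint, sample size or decision rule of the randomized extension depends on it.

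**Working it through.** **1. Which rule applies?** Side by side in Protocol 12.1:

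- Under the CR and PR definitions, a non-randomized study needs confirmation. Cohorts 2A (non-randomized), 2B, 3A and 3B are non-randomized, so they would need it if the sentence is read by cohort.
- Under the confirmation paragraph, the trial must be non-randomized and have response as its primary endpoint. Protocol 3.2.1 makes safety primary for phase 1 and the 6-month progression-free rate primary for phase 2, so these cohorts would not need it.
- That paragraph explains its remaining circumstances by naming only randomized trials and studies with stable disease or progression as primary endpoint. A single-arm cohort with safety as primary endpoint is in neither group, so it is not clearly covered.

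The text supports two readings, and the SAP matches the more lenient one.

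**2. How many patients are affected?** Counts from SAP 4.2:

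- Non-randomized: 26 + 7 + 13 + 5 = 51. The 26 include 2 patients from Cohort 1.
- Randomized: 13 + 2 + 4 = 19.
- Total: 51 + 19 = 70, which reproduces the total in the protocol synopsis. Share non-randomized: 51/70 = 72.9%.

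**3. Effect of one response that fails confirmation.** The change in ORR is 1/n.

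| Cohort | n | 1/n, percentage points |
|---|---|---|
| 2A non-randomized | 26 | 3.8 |
| 2B | 7 | 14.3 |
| 2 (2A + 2B) | 33 | 3.0 |
| 3A | 13 | 7.7 |
| 3B | 5 | 20.0 |
| 3 (3A + 3B) | 18 | 5.6 |
| 2 + 3 | 51 | 2.0 |

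SAP 7.8 also splits 2A by the extended eligibility criteria. Each part has fewer than 26 patients if both are non-empty, so the step there exceeds 3.8 points.

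**4. Check of the interval method, then an illustration.** The planned Clopper-Pearson 95% interval reproduces both ORRs cited in Protocol 1.2: 9/39 gives 23.1% (11.1 to 39.3) and 3/50 gives 6.0% (1.3 to 16.5). With response counts assumed purely for illustration in Cohort 2A:

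- 6/26 = 23.1% (9.0 to 43.6)
- 5/26 = 19.2% (6.6 to 39.4)
- 4/26 = 15.4% (4.4 to 34.9)

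**5. Range for the unknown.** The documents do not give the share f of first-recorded responses that would fail confirmation. Assume f between 0 and 30%. Confirmed ORR = unconfirmed ORR × (1 − f), so an unconfirmed 20% becomes 14% to 20%. SAP 4.3 treats two interesting outcomes among 15 patients as a signal. Counting responses only, P(at least 2 of 15) = 1 − (1 − p)^15 − 15p(1 − p)^14, which is 0.833 at p = 0.20 and 0.642 at p = 0.14. The actual rule also admits outcomes other than response, so these figures show sensitivity and are not operating characteristics of the trial. At f = 0 nothing changes.

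**The case against.** The best defence is that the confirmation paragraph is the full rule and the sentences under CR and PR are shorthand for it. Those sentences say where confirmation is needed at most, and they speak of studies, not cohorts. Response is primary nowhere in Protocol 3.2.1, so on this view the SAP is simply compliant. This carries real weight. A reader might infer that the SAP contradicts the protocol, and the documents do not support that. What remains is that the paragraph's own list of exempt designs leaves out single-arm cohorts with safety as primary endpoint.

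For iRECIST the defence is stronger. The sentences requiring confirmation sit in the RECIST 1.1 part, and Table 9 is adopted without any exception by cohort, so the iPR/iCR waiver agrees with the protocol, although the table's randomized premise does not describe these cohorts.

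The plan is also open about its choice. It gives exact intervals and waterfall plots and lists all response assessments (SAP 7.8.3). No formal comparison with a historical rate appears in the readable text, and the protocol does not say whether the two cited ORRs were confirmed. These points stand and limit the importance of the issue. However, listings leave the reader to derive the confirmed rate by hand.

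The objection that local reading is not the whole story stands in part. Protocol 7.7 says evaluation is primarily local and is followed by redacted text. The independent scan review in SAP 4.3 concerns progression in the randomized extension. Central review of response can be neither assumed nor excluded.

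**Conclusion.** The point holds as an unreconciled ambiguity in Protocol 12.1, with a one-directional risk to a secondary endpoint. Unconfirmed ORR can never be lower than confirmed ORR. The possible excess is 1/n per unconfirmed response, from 3.8 points in 2A to 20 points in 3B, across cohorts holding 51 of 70 patients.

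A reader might infer that the reported ORR is inflated. The documents do not show this, because they give no count of responses failing confirmation and that count may be zero. A reader might also infer from the SAP date (November 2024, after the initial part of Cohort 2 had been analysed) that the lenient rule was chosen with results in view. Nothing in the documents supports that. SAP 5.3, on changes from planned analyses, is unreadable, so it cannot be said that the choice went undeclared.

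The conclusion rests on the cohort counts in SAP 4.2 and on reading the CR and PR sentences as at least arguably applying to the non-randomized cohorts. It is a minor, inexpensive improvement.

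**What to change.** 1. Reconcile the CR and PR definitions in Protocol 12.1 with the confirmation paragraph, and state in SAP 7.8.3 which rule governs the non-randomized cohorts and why.
2. Keep the planned ORR as the main figure in all cohorts and label it unconfirmed in tables and text. Making a confirmed ORR the headline in the non-randomized cohorts alone would give 2A and 2A-I different definitions and redefine an endpoint late in an open-label trial.
3. For Cohorts 2A (non-randomized), 2B, 3A and 3B, add as a sensitivity analysis a confirmed ORR with exact 95% CI, counting a response as confirmed if it is maintained at the next scheduled 8-weekly CT. The readable protocol sets no confirmation interval for response, so this definition must be written into the SAP. Show separately the number of responders with no later scan.

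The cost is one derived variable from CTs already scheduled (SAP 7.8.1) and a column in the ORR tables. The confirmed figure may be lower, and a response first seen on a patient's last scan cannot be confirmed, so the confirmed rate may understate activity to that extent.

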**Table 7 : Integration of target, non-target and new lesions into response assessment**

Target Lesions	Non-Target Lesions	New Lesions	Overall Response	Best Response for this Category also Requires
Target lesions ± non target lesions				
CR	CR	No	CR	Normalization of tumour markers, tumour nodes <10 mm
CR	Non-CR/Non-PD	No	PR	
CR	Not all evaluated	No	PR	
PR	Non-PD/ not all evaluated	No	PR	
SD	Non-PD/ not all evaluated	No	SD	Documented at least once $\geq 4$ wks. from baseline
Not all evaluated	Non-PD	No	NE	
PD	Any	Any	PD	
Any	PD	Any	PD	
Any	Any	Yes	PD	
Non target lesions ONLY				
No Target	CR	No	CR	Normalization of tumour markers, tumour nodes <10 mm
No Target	Non-CR/non-PD	No	Non-CR/non-PD	
No Target	Not all evaluated	No	NE	
No Target	Unequivocal PD	Any	PD	
No Target	Any	Yes*	PD	
Note: Patients with a global deterioration of health status requiring discontinuation of treatment without objective evidence of disease progression at that time should be reported as "symptomatic deterioration". This is a reason for stopping therapy, but is NOT objective PD. Every effort should be made to document the objective progression even after discontinuation of treatment.				
*Investigators should record all new lesions; if the new lesion is felt to be equivocal, treatment may be continued pending further assessments – see table 2.				

[figure not shown]

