#### 4.3 Sample size

##### Cohorts 1, non-randomized 2A, 2B, 3A, and 3B

This is an early development, open-label, exploratory, multi-cohort trial to include patients with very rare malignant adrenal tumors; i.e. ACC and MPP. In this context, the sample size of the trial has been determined by practical considerations in collaboration with experts in the field, aiming at the possibility to recruit different patient populations to facilitate an as fast as possible, and broad (in relation to patient baseline characteristics), assessment of safety and tolerability, immunogenicity, and preliminary efficacy; [REDACTED]

[REDACTED] Based on these factors, the trial was designed to include an initial safety lead-in, 3-by-3 design, cohort including 3 to 12 patients, followed by 4 cohorts, including distinct patient populations, to be recruited in parallel each enrolling 15 patients evaluable for safety.

Patients in Cohort 1 who are evaluable [REDACTED] will, besides being part of Cohort 1, also be assessed as part of the planned Cohorts 2A or 3A. Thus, the number of evaluable patients to be recruited to Cohorts 2A and 3A might be decreased based on the number of evaluable patients already recruited in Cohort 1.

The 3-by-3 approach for Cohort 1 includes predefined stopping rules if concerning safety events would be encountered; in short 0 (zero) concerning safety event in 3 patients, or 1 concerning safety event in 6 patients, are considered acceptable.

The number of evaluable patients aimed at in Cohorts 2A, 2B, 3A, and 3B, i.e. 60 evaluable patients in total can in the context of adrenal malignancies be seen as a large dataset for safety assessments.

From an efficacy perspective, by inference from earlier clinical experience in the rare adrenal malignancies, it is judged that if there would be at least two interesting outcomes (which might be objective tumor responses, and/or assessable relevant biomarker responses, and/or prolonged Disease Control Rate (DCR) of  $\geq 6$  months for patients with ACC, and  $\geq 12$  months for patients with MPP) within one of the cohorts, i.e. within a group of 15 patients it would be an interesting outcome, and it could be considered to explore the treatment in further patients in a new trial (or via an amendment of the current trial).

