### 7.8.1 General aspects of response related endpoints

The response assessments during the treatment period follow the scheduled CTs post

baseline, planned for the visits at study weeks 9, 17, 25 (+/- 4 days), and from Week 25 onwards every 8 weeks (+/- 4 days). Unscheduled CT assessments as well as planned CT scans performed on the day of study drug administration [REDACTED]

[REDACTED] are also possible. For patients who are discontinuing all study treatment without having had confirmation of progressive disease (PD) according to iRECIST criteria [Seymour et al], CT assessments are scheduled every 8 weeks (+/- 4 days) after the latest performed CT assessment during the time period they received study treatment.

If not otherwise stated, all response assessments collected by investigator (local assessments) during the study will be considered, regardless of whether they come from scheduled or unscheduled assessments and if they were assessed during or after study treatment.

In principle, any further anti-cancer treatment during the study, i.e. prior to the individual study treatment termination, is prohibited. If nevertheless a patient is treated with further anti-cancer treatment during the study, the inclusion of CT assessments after introduction of further anti-cancer treatment in the derivation of response related and time to event endpoints will be agreed on and documented during the DRM. Also, the non-trial systemic anti-cancer treatments defined in Section 7.8.5 and 7.8.6 will be confirmed during the DRM.

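### The DCR in SAP 7.8.3 sets no minimum interval for stable disease, and no patient proportion is specified for the 6- or 12-month disease control named in SAP 4.3

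*SAP*

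**What the plan says.** **DCR definition.** SAP 7.8.3 gives two parallel rules. For iRECIST: "The DCR [%] is defined as the relative number of patients achieving at least one assessment of iCR, iPR, or iSD". For RECIST it defines the rate "as the relative number of patients achieving at least one assessment of CR, PR, or SD according to RECIST". Neither rule has a minimum interval or a minimum duration. Both rates are tabulated by cohort with exact Clopper-Pearson 95% intervals.

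**Scans that count.** SAP 7.8.1 uses all local response assessments, "regardless of whether they come from scheduled or unscheduled assessments and if they were assessed during or after study treatment".

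**Stable disease in the protocol.** Appendix 1 (12.1) gives an interval in two places. The text on confirmation and duration of response says that "measurements must have met the SD criteria at least once after study entry at a minimum interval", in general no shorter than 6 to 8 weeks, and leaves the value to the study protocol. Table 7 puts a condition on an SD best response: "Documented at least once" at 4 weeks or more from baseline. The iRECIST tables (Tables 8 and 9) print no interval.

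**The outcome of interest.** SAP 4.3, for the non-randomized cohorts, lists what might be an interesting outcome: objective responses, biomarker responses, or "prolonged Disease Control Rate (DCR) of" at least 6 months in ACC and at least 12 months in MPP. Two such outcomes among 15 patients could lead to further exploration.

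**Related analyses.** SAP 7.8.5 defines duration of disease control (DDC) in patients who have disease control. SAP 7.8.7 gives it Kaplan-Meier curves, a median and quartiles. The 6-, 12-, 18- and 24-month estimates in that section are for PFS and OS only.

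**The concern.** The SAP uses one name for two quantities. In 4.3, disease control counts as interesting when it lasts 6 or 12 months. In 7.8.3, one stable scan is enough, whatever the next scan shows. A reader who takes the tabulated DCR back to 4.3 would be comparing different things, and the tabulated rate is the more favourable of the two.

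The definition also drops a condition that the protocol's own response appendix attaches to stable disease. As written, an unscheduled CT read as stable soon after the first dose, followed by progression at week 9, counts as disease control.

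DCR has had some weight in this trial. The part of SAP 4.3 on the randomized extension cites ORR/DCR, together with PFS and early survival, as the interesting outcome that supported extending Cohort 2A.

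**Working it through.** The plan states no sample size, power or target that depends on DCR, so there is no planned figure to reproduce. The check has four parts.

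**1. Scan calendar.** SAP 4.4.1 equates week 25 with day 169. The rule day = (week − 1) × 7 + 1 reproduces this: 24 × 7 + 1 = 169. SAP 7.8.1 schedules CTs at weeks 9, 17 and 25, then every 8 weeks, each ± 4 days. With the SAP's conversion of 30.5 days per month:

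| Scheduled CT | Days from first dose | Months |
|---|---|---|
| Week 9 | 56 | 1.84 |
| Week 25 | 168 | 5.51 |
| Week 33 | 224 | 7.34 |
| Week 49 | 336 | 11.02 |
| Week 57 | 392 | 12.85 |

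**2. Effect of the missing interval.** The earliest in-window week-9 scan is at 56 − 4 = 52 days, or 52/7 = 7.4 weeks after first dose. Every scheduled scan therefore clears both 4 and 6 weeks. The early edge falls 4 days short of 8 weeks counted from first dose, but the baseline CT precedes first dose. Only an early unscheduled scan can breach the Table 7 condition.

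**3. Effect of the missing duration.** Stable disease at week 9 followed by progression counts as control after 1.84 months. That is 1.84/6 = 31% of the ACC duration in SAP 4.3 and 1.84/12 = 15% of the MPP duration. The week-25 scan, even 4 days late, is at 172/30.5 = 5.64 months. A strict 6-month limit is therefore first documented by a scheduled scan at week 33, and a strict 12-month limit at week 57.

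**4. Illustration of how far the measures can differ.** Protocol 1.2 reports the avelumab ACC trial: 3 partial responses and 21 stable among 50 patients, and median PFS 2.6 months (95% CI 1.4 to 4.0).

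- Any-time DCR: (3 + 21)/50 = 48.0%, which matches the protocol.
- 6-month PFS under an exponential curve (assumption), S(6) = 2^(−6/median): 2^(−6/2.6) = 0.202. At the CI limits, 2^(−6/1.4) = 0.051 and 2^(−6/4.0) = 0.354.
- In the 26 patients of non-randomized Cohort 2A: 26 × 0.48 = 12.5 against 26 × 0.202 = 5.3 (range 26 × 0.051 = 1.3 to 26 × 0.354 = 9.2).
- Ratio: 0.48/0.202 = 2.4, range 1.4 to 9.4.
- Chance of at least 2 in 15, 1 − (1−p)^15 − 15p(1−p)^14: 99.9% at p = 0.48 and 83% at p = 0.20.

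**What existing outputs cover.**

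| Output | Whole cohort as denominator | 6/12-month value | Patient count |
|---|---|---|---|
| DCR (7.8.3) | yes | no | yes |
| DDC (7.8.5, 7.8.7) | no | curve only | no |
| PFS (7.8.7) | yes | yes, Kaplan-Meier | no |
| 6-month PFS count (7.8.2) | yes | 6 months | tabulated for Cohort 2A-I |

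No row gives a count or proportion with control of at least 6 or 12 months in Cohorts 2A, 2B, 3A and 3B.

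**The case against.** **Durable control is already measured.** A reader might infer that the SAP leaves it unmeasured. The documents do not support that. The 6- and 12-month PFS estimates in 7.8.7 rest on the full analysis set and cover both horizons. A patient known to be progression-free on an evaluable scan at 6 months has had stable disease or better. This largely stands: what remains is a patient count, which a Kaplan-Meier estimate with censoring does not supply.

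**SAP 4.3 is not a decision rule.** It is sample-size rationale, with alternatives and permissive wording, and has no threshold rate or error rate. The extension of Cohort 2A has already happened, and the cohorts recruited 26, 7, 13 and 5 patients rather than 15 each. This stands. DCR is not among the visible primary or secondary endpoints, so it is not a headline result with a target that has been made easier.

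**The interval hardly matters, and the protocol gives no single value.** Both points stand. One can also argue that 7.8.3 imports the Table 7 condition by referring to RECIST. That is a possible reading, but counting any one SD assessment points the other way. Two protocol values and none for iRECIST are a reason for the SAP to state one.

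**The illustration compares two different endpoints.** Any-time DCR will normally exceed 6-month PFS, and the avelumab DCR is also an any-time rate, so the present definition keeps comparability with it. This stands, and it is a reason to keep that rate.

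**Redaction.** The exploratory endpoints and the changes to planned analyses are blacked out, and the table shells are in separate appendices. A duration-based row could exist there.

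**Conclusion.** The point holds in a limited form. The DCR in SAP 7.8.3 omits the protocol's interval condition for stable disease, and it is not the durable control that SAP 4.3 names. No patient proportion with control of that length is specified for the non-randomized cohorts in the visible text.

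The interval gap is small, since it touches only early unscheduled scans. The duration gap is one of reporting, since DDC and the PFS landmarks come close.

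The 48% against about 20% shows that the two measures can differ. It does not show that any stated figure is wrong. It rests on an assumed exponential curve and one cited trial, and the 6-month value runs from about 5% to 35% over the confidence interval of the median. A reader might infer that DCR overstates activity by a factor above 2; the range of 1.4 to 9.4 does not support a fixed factor. The signal of two in 15 would also be likely at either rate (99.9% and 83%).

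No primary analysis, error rate or sample size changes.

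**What to change.** 1. **State the interval in SAP 7.8.3.** Count SD or iSD only if it meets one stated minimum interval from baseline. Keep it consistent with Table 7, reconcile it with the 6-to-8-week text in Appendix 1, and say that it applies to iSD as well.
2. **Add one row per table.** Give n/N with an exact 95% CI for disease control lasting at least 6 months (ACC) and at least 12 months (MPP), with all FAS patients in the cohort as denominator. State how scan windows map to these limits, because the week-25 scan falls at about 5.5 months although SAP 4.4.1 ties the 6-month primary endpoint to it. State how patients censored before the limit are counted. Refer to this row wherever SAP 4.3 is discussed.
3. **Keep the present rate, labelled any-time DCR**, for comparison with published rates.

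The cost is some SAP wording and one extra row per table from data already collected. The added control rate will look less favourable than the any-time DCR.
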